5.1.2 Figures

- Bar charts: OspA-specific IgG antibodies (GMT) including standard deviation vs OspA serotypes by treatment group for each time point separately (y-axis: GMT; x-axis: OspA STs per treatment groups)
- Bar charts Seroconversion Rate:
 - Seroconversion Rate by OspA serotype and treatment group (for each time point separately, y-axis: percentage of subjects, x-axis: OspA STs per treatment groups)
 - Seroconversion Rate for all OspA serotypes combined over time vs. treatment group (y axis: percentage of subjects, x axis: visits per treatment groups)
 - Seroconversion Rate for OspA serotypes ST1 and ST2 combined over time vs. treatment group(y axis: percentage of subjects, x axis: visits per treatment groups)
- Line charts (y-axis: GMT, x-axis: study days): OspA- specific IgG antibodies (GMT) over time vs. treatment group for each ST1-6 separately
- Line charts (y-axis: GMT, x-axis: study days): OspA- specific IgG antibodies (GMT) over time vs. serotype for each treatment group separately
- For each OspA serotype and treatment group: Reverse cumulative distribution curves: percentage of subjects vs. OspA specific
- Scatter plots representing the correlation between OspA IgG antibody GMTs for each combination of two different OspA specific IgG serotypes for all treatment groups pooled.

5.2 Derivations and Definitions

- Baseline for immunogenicity analysis is defined as Visit 1.
- A subject reaches a 4-fold increase if the value at a certain visit after Day 1 is at least 4-times higher than the value at Day 1. 10-fold increase will be derived analogously.
- Baseline OspA IgG seropositive/seronegative for ELISA is defined as follows:
 - ELISA samples scored as “negative” or below the quantitation limit of the ELISA (40 U/mL) will be replaced by 20 U/mL.
 - Subjects with Day 1 (Visit 1) values below the quantitation limit of the ELISA (40 U/mL) and samples scored as “negative” (i.e. replaced by 20 U/mL) will be considered “baseline OspA IgG seronegative” for each serotype.

- Subjects with Day 1 (Visit 1) values of 40 U/mL and above are considered “baseline OspA IgG seropositive” for each serotype.
- Seroconversion is defined as:
 - For subjects that are seronegative at Visit 1 (baseline): a change from seronegative at Visit 1 to seropositive (i.e. antibody titer of ≥ 40) at a certain time point.
 - For subjects that are seropositive Visit 1 (baseline): a ≥ 4 -fold rise in IgG antibody titer from Visit 1.
 - In case of missing values (missing at baseline or current time point), seroconversion is not calculated.

5.3 Inferential analysis

- In general, all statistical tests comparing treatment groups in the immunogenicity analysis will only include the two dose groups chosen for the main phase (i.e. VLA15 135 μ g and 180 μ g groups) and the placebo group. However, summary measures for 90 μ g group will be included in the tables.
- ANOVAs with factors treatment group and study sites will be performed for the comparison between the VLA15 135 μ g, 180 μ g and Placebo group for each OspA ST1 to ST6 respectively. The primary immunogenicity analysis will be the ANOVA for ELISA GMTs at Day 85 in the PP Population.
- ANOVAs will be performed for GMTs as well as GMFRs at all available time points.
- This will be done using log10 transformed data and taking the anti-log of the resulting point estimates for the least squares means, least squares means differences and the corresponding 95% CIs. Tukey's HSD test will be applied for pair-wise comparisons.
- Sensitivity analyses for GMTs and GMFRs will be performed for ANOVAs with factors study site, treatment group, study site*treatment group, age, and B.b. s.I serostatus at baseline.
- Summary tables for the OspA- specific IgG titer against each OspA serotype and summary tables for the geometric mean fold-rise against each OspA serotype will be amended by an overall test (Kruskal-Wallis).
- SCRs will be compared using Fisher-Freeman-Halton tests, a significant overall test will be amended by pair-wise tests (Fisher's exact test). The same will be done for rates of subjects reaching a 4- or 10- fold Increase from Day 1 (Visit 1) in titer.
- A non-parametric correlation analysis (Spearman) between OspA IgG antibodies GMTs for each combination of two different OspA specific IgG types will be performed for Day 85 and VLA15 treatment group separately as well as for all VLA15 treatment groups together (pooled analysis).

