1.4 Sample Size Calculation

The sample size for the Run-in phase has been chosen to allow detection of common AEs with the three initial dose levels. 30 Subjects will provide 95 % confidence that an AE not seen in the Run-in phase would have a true incidence of below 10 %.

The overall group size for the two doses (VLA15 w/ alum 135 µg and VLA15 w/ alum 180 µg) evaluated in the Main Study phase has been selected to provide a sufficient safety database and for determining the optimal dose before advancing the vaccine candidate into Phase 3. Upon completion of the study, the total number of subjects exposed to the dose used for Phase 3 trials would be a minimum of approximately N=210. The database would thus allow 95 % confidence that a given reaction would not be observed at a higher rate than 1:(210/3) rate, i.e. 1.4 %, if it is not observed in the trials preceding Phase 3.

[figure not shown]
With respect to the primary endpoint, GMTs for ST1-6 specific IgGs on Day 85: In the absence of an established protective titer, sample size calculation is based on somewhat arbitrary differences in GMTs between VLA15 treatment groups, in order to demonstrate which titer levels could be distinguished with the proposed sample size. Titers observed in Phase 1 were used as basis: In the 90 µg w/ alum group (i.e. the lowest dose group used in the present Phase 2 study), a GMT of 61.3 was observed for ST1 (i.e. the serotype with lowest titers in Phase 1) with a Standard Deviation (LOG10) of 0.51. A total of 189 subjects per group (assuming 10 % of the 210 subjects per treatment group are excluded from primary Per-protocol (PP) analysis) will provide 80 % power at a two-sided alpha level of 5 % to distinguish a GMT of 61.3 in one treatment group from a putative higher GMT of 86.1 in another dose group. An approximately 1.5 fold higher titer could thus be distinguished. A 1.5 fold difference in GMTs is often considered a relevant difference in vaccine studies, e.g. when setting non-inferiority boundaries.

The overall sample size of 120 subjects in the placebo group has been selected to allow for the internal validation of both safety and immunogenicity results.

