2.4 Blinding and Randomization

Subjects will be allocated to treatment groups via the EDC system. Eligible subjects will be randomized stratified by study site 1:1:1:1 in the Run-in Phase and stratified by study site, age group and baseline *B.b. s.l.* serostatus 2:2:1 in the Main Study Phase according to a randomization list created by a statistician. The study will be an observer-blinded trial, which will be conducted in a blinded manner for the study investigators, the sponsor including laboratory personnel, and the subjects. Only designated study staff who randomize subjects into treatment groups and perform preparation and application of the vaccinations will be unblinded. These unblinded study staff members will not be involved with trial conduct otherwise. An overview of persons who will be unblinded is provided below:

Unblinded:

- Designated study site staff who randomize subjects to treatment groups and are concerned with IMP handling (i.e. perform preparation and application of the study vaccine, maintain drug dispensing log detailing the dates and quantities of IMP administered to each subject). These unblinded study staff members will not be involved with trial conduct otherwise.
- CRAs responsible for monitoring of IMP handling and related data for verifying drug accountability during the study and performing overall drug accountability.
- Statistical team at the CRO performing statistical analyses for generation of safety data tables for the DSMB.
- DSMB members.

Blinded:

- Study participants
- Investigators and other study staff involved in general study conduct and safety assessments.
- All other CRAs (responsible for monitoring study data apart from IMP handling/drug accountability).
- All other sponsor and CRO staff including laboratory personnel at the sponsor's labs for immunogenicity assessments.

General unblinding of sponsor staff and ADMB will be done for the IA Day 85 after confirmation that all subjects performed Visit 6 or, in case of missing V6 visits, after the close of the time window for Visit 6. Interim analyses results will be distributed to selected sponsor representatives.

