2.5 Descriptive Analyses

In general, descriptive analyses of continuous variables (summary statistics) will be described with the number of non-missing observations, arithmetic mean, standard deviation (\pm SD), median, quartiles (Q1 and Q3) and range (minimum and maximum).

Descriptive analyses of continuous immunogenicity variables (i.e. tables for the GMT and GMFR) will be described with the number of non-missing observations, geometric mean, confidence intervals for the geometric mean, standard deviation of logarithmic values, median, quartiles (Q1 and Q3) and range (minimum and maximum).

Categorical variables (frequency statistics) will be described with the number of non-missing observations and percentages (%). Percentages will be calculated on the total number of non-missing observations, if not stated otherwise.

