2.14 Changes in the Conduct of the Study or Planned Analysis

Statistical analysis will be conducted as described in this SAP. Any deviations or changes will be described and justified in the CSR.

- It was stated in the protocol that an interim analysis on safety and immunogenicity data will be performed after all subjects have completed Visit 6 (i.e. Day 236, six months after the last vaccination) and that this interim analysis will cover safety and immunogenicity data up to Visit 4 as well as safety data up to Visit 6. This interim analysis will be conducted in 2 parts, a IA Day 85 covering all safety data up to Day 85 and immunogenicity data from Day 1 and Day 85. The second part will cover all safety data up to Day 236 (see Section 2.1). The first part of the Interim Analysis only starts after the last subject completed Visit 6 or the time window for Visit 6 has elapsed.

- The following adjustments concerning statistical analysis as compared to descriptions in the protocol are included in this SAP: The protocol planned to only compare the two dose groups selected for the main phase and the placebo group. However, it was decided to include all dose groups in the comparison. In particular, the pair-wise comparison between the two dose groups selected for the main phase and the placebo group, respectively, will be part of the comparisons that will be performed.
- It was stated in the protocol that all time points up to Day 85 will be included in interim immunogenicity analysis. However, only Day 1 and Day 85 will be analyzed in the IA Day 85. All time points will be analyzed in the Final Analysis.
- Due to optimization of the ELISA assay, the definition for seroconversion for ELISA results was adjusted as compared to the protocol, see Section 5.2.
- Functionality of antibodies will be measured by a Serum Bactericidal Assay (SBA). Analysis of SBA parameters will be described in a separate SAP and is not part of the interim analysis described here.

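### The primary Day 85 ANOVA pools placebo and dose-group variances, so dose-group standard errors come out about 7.5-11.8% too small if placebo titers vary little (placebo SD assumed)

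*SAP*

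**What the plan says.** Section 5.3 defines the primary immunogenicity analysis, for ELISA GMTs at Day 85 in the PP Population: "ANOVAs with factors treatment group and study sites will be performed for the comparison between the VLA15 135" µg, 180 µg and placebo groups, separately for each of ST1 to ST6. Data are log10 transformed, and the reported results are the anti-logs of the "resulting point estimates for the least squares means, least squares means differences and the corresponding 95% CIs". For pairs, Tukey's "HSD test will be applied for pair-wise comparisons". GMFRs are analysed the same way. The section names no group-specific variance, robust standard error or variance check, and does not say whether the difference CIs are Tukey-adjusted.

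Three other places matter:
- Section 5.2: samples scored negative or "below the quantitation limit of the ELISA (40 U/mL) will be replaced by 20 U/mL".
- Section 1.4: the only SD given, for a Phase 1 90 µg group and ST1, "with a Standard Deviation (LOG10) of 0.51". No placebo SD is given.
- Section 2.14: "Due to optimization of the ELISA assay, the definition for seroconversion for ELISA results was adjusted". The Phase 1 SD may therefore not carry over to the current assay.

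**The concern.** A standard ANOVA has one residual variance. Placebo is PBS, and unexposed placebo subjects will mostly share the value 20 U/mL, so their log10 spread should be small. Vaccinated subjects will spread widely. Pooling the two gives an error term too small for the dose groups and too large for placebo.

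The primary objective is to find the optimal dose, and in the primary model that means 135 vs 180 µg. Placebo carries no information on how variable vaccinated titers are, yet it makes up 22.2% of the subjects who set the precision of that contrast. The model can report dose-group CIs that are too narrow, and placebo and dose-vs-placebo CIs that are too wide.

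GMFR is exposed to the same problem. A placebo subject at 20 U/mL on both Day 1 and Day 85 has a log fold rise of exactly 0.

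**Working it through.** **Inputs.**
- Dose-group log10 SD (sd): 0.51, section 1.4.
- PP size per dose group: 189 (210 less 10%), section 1.4.
- Placebo: 120 in section 1.4, so 108 if the same 10% exclusion applies (assumption).
- Placebo log10 SD (sp): not in the SAP; varied below.

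**The SAP's own figure.** log10(86.1/61.3) = 0.1475. SE = 0.51 × sqrt(2/189) = 0.0525. Power = Phi(0.1475/0.0525 − 1.96) = 80.3%, so the stated 80% reproduces. That calculation uses the dose-group SD alone.

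**Plausible placebo SD.** If 10% of placebo subjects sit at X U/mL and the rest at 20, SD = sqrt(0.1 × 0.9) × log10(X/20). This gives 0.21, 0.30 and 0.39 for X = 100, 200 and 400. To reach 0.51, X would have to be about 1,000 U/mL.

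**Pooled error term.** With three groups and before the site terms, df = 188 + 188 + 107 = 483, and

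MSE = (376 × sd² + 107 × sp²)/483, r = sqrt(MSE)/sd.

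Here r is the model SE divided by the true SE, for a dose-group LS mean and for the 135 vs 180 µg difference. Unadjusted coverage = 1 − 2 × (1 − Phi(1.965 r)). The Tukey critical value for three groups is 2.351, so the Tukey error for 135 vs 180 µg = 2 × (1 − Phi(2.351 r)). At sd = 0.51:

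| sp | r | SE too small | Unadjusted 95% CI covers | Tukey error, 135 vs 180 |
|---|---|---|---|---|
| 0 | 0.882 | 11.8% | 91.7% | 3.8% |
| 0.20 | 0.901 | 9.9% | 92.3% | 3.4% |
| 0.30 | 0.925 | 7.5% | 93.1% | 3.0% |
| 0.40 | 0.956 | 4.4% | 94.0% | 2.5% |
| 0.51 | 1.000 | 0% | 95% | 1.9% |

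Group sizes of 210/210/120 give the same r. The placebo CI is 0.51 × 0.901/0.20 = 2.3 times too wide at sp = 0.20, and 0.51 × 0.925/0.30 = 1.6 times at sp = 0.30.

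**Other dose SDs.**
- sd 0.40: 11.8, 8.7, 5.0 and 0% too small at sp 0, 0.20, 0.30 and 0.40.
- sd 0.35: 11.8, 7.8 and 3.0% too small at sp 0, 0.20 and 0.30; at sp 0.40 the SE is 3.3% too large.
- If 0.51 is the SD before the 20 U/mL replacement, a dose GMT of 61.3 gives SD 0.465 after it, and 6.7% at sp 0.30.

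**Simulation with site fitted.** One run used 40,000 trials per placebo SD, 10 balanced sites and sd 0.51. SE ratios were 0.88-0.93 for sp 0 to 0.30, matching the formula. The family-wise Tukey error, with no difference between any groups, was 3.6-3.9%.

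A second run used 18 scenarios of 4,000 trials each, with 8 or 15 sites, no true site effect, and the 20 U/mL replacement applied. Dose SDs before replacement were 0.51 or 0.35. Ranges over the scenarios:

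| Quantity | Planned model | Alternative |
|---|---|---|
| 135 µg LS-mean coverage | 91.1-94.0% (SD 0.51), 92.0-95.0% (SD 0.35) | 94.4-95.5% (two dose groups plus site) |
| 135 vs 180 µg coverage, unadjusted | 91.4-93.4% (SD 0.51), 92.0-94.2% (SD 0.35) | 94.5-95.6% (two dose groups plus site) |
| 135 µg vs placebo coverage, unadjusted | 96.6-99.7% | 94.6-96.2% (three groups, HC3) |
| Tukey error, 135 vs 180 µg | 2.2-4.2% | not run |

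A further check, with and without true site effects, put coverage of the 135 vs 180 µg difference at 92-93% as planned and about 95% under either alternative.

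**The case against.** The strongest reply is that no wrong dose decision follows. Point estimates do not move, the planned Tukey test of 135 vs 180 µg stays below 5%, and the SAP sets no CI-based rule for choosing a dose. If the difference CIs are Tukey-adjusted, they cover 96.2-97.0% at placebo SD 0 to 0.30, and only the single-group LS-mean CIs fall short. The ratio CI moves only from x/÷ 1.23-1.25 to x/÷ 1.27, while section 1.4 treats about 1.5-fold as relevant. All of this stands and limits the weight of the point.

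The size also rests on SDs the SAP does not give, and the direction can reverse. That stands too, although a reversal needs placebo to vary more than the vaccinated groups.

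The 20 U/mL replacement is listed under the baseline serostatus definition. Applying it at Day 85 is an inference, supported by Listing 16.1.3.1, which separates measured from analysis titers.

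Section 2.14 says all dose groups will be compared, against section 5.3. With about 27 PP subjects at 90 µg in the model, the shortfall is 7.1-11.1%, so the conclusion is unchanged.

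Nothing else planned repairs the problem. The sensitivity ANOVAs add covariates and a site interaction but keep the common variance. Kruskal-Wallis is an overall test without a dose-contrast SE. The descriptive tables (section 2.5: "geometric mean, confidence intervals for the geometric mean, standard deviation of logarithmic values") use each group's own spread and will show the inequality, but give no dose contrast and no site adjustment.

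**Conclusion.** The concern holds. With dose SD 0.51 and placebo SD 0 to 0.30, the primary model understates the standard errors of the dose-group LS means and of the 135 vs 180 µg difference by 7.5-11.8%. At placebo SDs between 0.30 and 0.51 the shortfall falls from 7.5% to 0. The LS-mean CIs undercover on any reading of section 5.3; the difference CI undercovers only if it is not Tukey-adjusted, which the SAP leaves open.

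This rests on an assumed placebo SD, on a Phase 1 SD from another dose group, on the 10% PP exclusion also applying to placebo, and on the 20 U/mL replacement at Day 85. The effect is modest and threatens neither the point estimates nor the Tukey test. It should still be corrected, because it affects the error bars of the primary analysis and is cheap to remove. No separate calculation was run for GMFR; the same mechanism applies there.

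**What to change.** In section 5.3:
- Estimate the VLA15 LS means and the 135/180 µg ratio, with 95% CIs, from an ANOVA on the two VLA15 groups plus study site.
- Compare each dose with placebo, for all six serotypes, by the three-group model (treatment, site) with HC3 standard errors, prespecified with no data-driven switching. It still works if every placebo value is 20 U/mL: simulated coverage was then 95.0-96.2%.
- State whether the difference CIs are multiplicity-adjusted. If family-wise control over the three pairwise tests is kept, name one adjustment, for example Holm. Under Holm, once both placebo comparisons reject, 135 vs 180 µg is tested at the full 5%; family-wise control holds, but the test is not stricter than now.
- Do the same for GMFR.

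The cost is a few lines of SAS and SAP text. At dose SD 0.51 the unadjusted ratio limit is 10^(1.965 × 0.0525) = x/÷ 1.27, against 1.23-1.25 under pooling with placebo SD 0 to 0.30. Site effects for the dose contrast come from VLA15 recipients only, so dose LS means may differ slightly from those implied by the placebo contrasts; the SAP should say which are reported as primary.

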(2) Occurs before screening and prior to any study-related procedures.

Adapted from:

STAT03_A Statistical Analysis Plan
Version 6.0, Effective Date 16-Feb-2018
Confidential and intellectual property of [REDACTED]

No part of this document or its contents may be duplicated, referenced, published or otherwise disclosed in any form or by any means without prior written consent of [REDACTED]

(3) Symptoms noted at Visit 1 (prior to first vaccination) are not considered AEs but will be recorded as medical history.

(4) Physical examination on following body systems: general appearance, skin, head/abdomen, extremities and joints, lymph nodes, and neurological system. If applicable, physical examination as well as ECG performed within the study VLA15-202 is acceptable for study VLA15-201 if within the specified visit window.

(5) Vital signs (Systolic and diastolic blood pressure and pulse rate while seated and at rest) to be measured prior to vaccination and in addition prior to discharge in case subject reports any complaints.

(6) To be performed prior to vaccination.

(7) The results of negative HIV tests that were performed up to 30 days before Visit 0 are acceptable (blood: HIV test 3.5 mL). Positive HIV test obtained by ELISA will have to be confirmed by a second method (e.g. Westernblot or PCR).

(8) A commercially available C6 ELISA assay (ViSE ELISA) will be performed (blood: 4 mL). Serum samples that are tested positive will have to be verified by a confirmatory immunoblot. Test results need to be available before randomization and remain valid for 4 weeks.

(9) A baseline serology sample will be taken in the screening visit and might be used for work-up of suspected LB-associated, autoimmune or neuroinflammatory events (e.g. analysis of Rheumatoid factor (RF), anti-citrullinated protein antibodies (ACPA), etc. as appropriate), (blood: 5.0 mL). If applicable, a baseline serology sample collected at the study site within the study VLA15-202 is acceptable for study VLA15-201 if within the specified visit window.

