2. GENERAL CONSIDERATIONS

2.1 Conduct of Analysis

An interim analysis (IA) on safety and immunogenicity data will be conducted in two parts after the last subject completed Visit 6 (i.e. Day 236). The first part (IA Day 85) will be performed after safety data up to Day 85 have been cleaned and immunogenicity samples of Day 1 and 85 have been analyzed. The first part (IA Day 85) will cover safety data up to Visit 4 (Day 85) and ELISA immunogenicity data from Visit 1 (Day 1) and Visit 4 (Day 85). The second part (IA Day 236) will cover safety data up to Visit 6 (Day 236, i.e. six months after the last vaccination).

Data from selected dose groups in the Main Study and data from respective dose groups from the Run-in phase will be pooled for this and all further analyses.

A preliminary immunogenicity analysis was done prior to the IA D 85 as described above. This analysis was described in a separate analysis plan and covered descriptive immunogenicity analysis of selected time points of subjects from the run-in phase only.

A final data analysis will be conducted once the last subject has completed the study, i.e. Visit 7 (Month 12). As part of this analysis, Serum Bactericidal Assay (SBA) results will be analyzed. Those results will only be available for a subset of subjects, that was randomly chosen from the set of subjects from the main phase who have both a Day 1 and Day 85 immunogenicity blood sample.

It is indicated in Section 7, which Tables, Listings and Figures (TLFs) are provided for IA D85 and IA D236.

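### No GMT or GMFR model adjusts for the Day 1 OspA titre as a covariate, so the dose contrast gives up some precision that is available at almost no cost

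*SAP*

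**What the plan says.** Section 5.3 of the SAP fixes the main model: "ANOVAs with factors treatment group and study sites will be performed for the comparison between the VLA15" 135 µg, 180 µg and placebo groups, serotype by serotype, on log10 data. It then names the governing analysis: "The primary immunogenicity analysis will be the ANOVA for ELISA GMTs at Day 85 in the PP Population". The same section adds "ANOVAs will be performed for GMTs as well as GMFRs at all available time points".

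The wider model is described as follows: "Sensitivity analyses for GMTs and GMFRs will be performed for ANOVAs with factors study site, treatment group, study site*treatment group, age", together with B.b. s.l. serostatus. Tables 14.1.3.1.30-53 in Section 7.1.3 list these factor sets and no others.

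On baseline, Section 5.2 says "Baseline for immunogenicity analysis is defined as Visit 1" and that results scored negative or "below the quantitation limit of the ELISA (40 U/mL) will be replaced by 20 U/mL". Section 2.1 puts "ELISA immunogenicity data from Visit 1 (Day 1) and Visit 4 (Day 85") in the first interim analysis. Serostatus comes from screening, where footnote 8 to the study schedule in Section 1.5.2 says "A commercially available C6 ELISA assay (ViSE ELISA) will be performed (blood: 4 mL"), with an immunoblot to confirm positives.

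**The concern.** The Day 1 titre of the same serotype is the obvious covariate for a Day 85 titre, and it costs nothing extra to obtain. The plan uses it only inside responses: the fold rise, and the binary endpoints derived from fold rise or seroconversion. On the log scale the GMT ANOVA fixes the coefficient of Day 1 at 0, and the GMFR ANOVA fixes it at 1. If the true slope lies between the two, both are less precise than a model that estimates it.

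Serostatus does not fill the gap. It is one yes/no flag per subject from a C6 assay, whereas Section 5.2 defines OspA status separately for each serotype from the trial's own ELISA.

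At stake is the precision of the 180/135 GMT ratio, which is the main evidence for the dose choice named as the primary objective.

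**Working it through.** **The plan's own figure.** Section 1.4 gives GMTs of 61.3 and 86.1, a log10 SD of 0.51, 189 per group (210 × 0.9) and two-sided 5%.
- Difference: log10(86.1/61.3) = 0.1475, a ratio of 1.405.
- Standard error: 0.51 × √(2/189) = 0.51 × 0.1029 = 0.0525.
- Power: Φ(0.1475/0.0525 − 1.96) = 80.3%.

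The stated 80% reproduces, without a covariate and without the Tukey adjustment. Tukey's adjustment is a separate matter and does not change the variance ratios below.

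**Formulas.** Let s be the SD of log10 Day 1 titre and β the slope of log10 Day 85 on log10 Day 1.
- GMT ANOVA variance: 0.51² = 0.2601.
- ANCOVA variance: 0.2601 − β²s².
- GMFR ANOVA variance: 0.2601 + s² − 2βs².

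**Assumptions, because the SAP gives neither s nor β.** A share of subjects is OspA-positive at Day 1, with geometric mean 80 to 150 U/mL and log10 SD 0.3, and no value below 40. All others sit at 20 U/mL. This gives s of about 0.205 to 0.28 at 10% positive, and about 0.095 to 0.13 at 2% positive.

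**Results.**

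| Positive share | s | β | ANCOVA variance | GMT ANOVA / ANCOVA | ANCOVA power |
|---|---|---|---|---|---|
| 10% | 0.205 | 0.5 | 0.2601 − 0.0105 = 0.2496 | 1.04 | 81.9% |
| 10% | 0.28 | 0.5 | 0.2601 − 0.0196 = 0.2405 | 1.08 | 83.3% |
| 2% | 0.095 | 0.5 | 0.2601 − 0.0023 = 0.2578 | 1.01 | 80.6% |
| 2% | 0.13 | 0.5 | 0.2601 − 0.0042 = 0.2559 | 1.02 (1.6% more) | 80.9% |
| any | any | 0 | 0.2601 | 1.00 | 80.3% |

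In the first two rows the saving is 189 × 0.0105/0.2601 ≈ 8 and 189 × 0.0196/0.2601 ≈ 14 subjects per arm. At β = 0.5 the GMFR ANOVA has the same variance as the GMT ANOVA, because s² − 2(0.5)s² = 0.

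**Effect of a chance baseline imbalance (10% positive).** One standard error of the Day 1 difference between the dose groups is s × 0.1029 = 0.021 to 0.029 log10. It enters the GMT contrast multiplied by β. At β = 0.5 this is 0.0105 to 0.0144, which moves the ratio by about 2-3%. The GMT and GMFR contrasts, in subjects with both values, differ by the whole imbalance: 10^0.021 to 10^0.029, or 5-7%.

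**Why one ANCOVA serves both endpoints.** If log Y85 = α + τ + β log Y1, with site terms included in α, then log Y85 − log Y1 = α + τ + (β − 1) log Y1. The treatment term τ is the same in both.

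**The case against.** The strongest reply is that nothing here is wrong. A treatment-plus-site ANOVA on log10 titre is valid under randomisation, the trial was sized for it, and its interval already reflects chance baseline differences. That stands in full. A reader might infer that the primary ratio is biased or the power figure wrong, and the SAP supports neither inference.

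A reader might also infer that the plan leaves two rival dose contrasts with no rule between them. It does not. Section 5.3 makes the Day 85 GMT ANOVA primary, and Section 1.3 makes the Day 85 GMT the primary endpoint and GMFR a secondary one.

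Three limits on the argument also stand:
- Missing Day 1 values are foreseen in Section 5.2, so the titre is planned for every subject but not guaranteed.
- The only 10% in the SAP is the enrolment target for B.b. s.l. seropositivity (Section 1.2). It is not an OspA share. Main Study randomisation is stratified by that serostatus, so enrichment alone does not show OspA imbalance.
- If most subjects sit at the 20 U/mL floor, Day 1 carries little information and the gain nearly vanishes.

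One might fear that a slope shared with placebo harms the dose contrast. As an unfavourable case, assume slope 0 in the vaccine groups and 1 in placebo, with 108 of 486 subjects on placebo (120 × 0.9, plus 2 × 189). The pooled slope is then about 0.22, and the added variance is 0.22²s²/0.2601, or 0.8-1.5% for s of 0.20 to 0.28. A separate placebo slope is therefore not required.

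What the reply does not answer is why a defined, assayed baseline should stay out of every model.

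**Conclusion.** The omission is real and worth correcting, as an improvement in precision. Under the assumed 10% OspA-positive share and slope 0.5, the present contrast carries about 4-8% more variance than ANCOVA, and power rises from 80.3% to about 82-83%. With about 2% positive the gain in variance is under 2%, and at slope 0 there is none. Larger gains need a steeper slope or more positives, for which the SAP gives no evidence. The change is still justified because it uses data already in hand and can cost the dose contrast very little.

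**What to change.** In Section 5.3 and Tables 14.1.3.1.30-41, add log10 Day 1 titre of the same serotype as a covariate in the Day 85 log10 titre model, with values below 40 U/mL set to 20 as in Section 5.2. Use observed Day 1/Day 85 pairs, in line with the no-imputation rule of Section 2.7, and read the 180/135 ratio from this model. Where Tables 30-35 report Day 1 itself, the covariate does not apply.

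Keep the present treatment-plus-site ANOVA as a sensitivity analysis, which also covers subjects without a Day 1 value. Label the GMFR ANOVAs (Tables 14.1.3.1.42-53) supportive, and state that the adjusted contrast is the same for GMT and GMFR.

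The cost is SAP wording, one model term in existing programs, and the loss from the adjusted model of the few subjects with no Day 1 value. No new data are needed.
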